3. PATIENT SELECTION

3.1 Eligibility Criteria

Participants must meet the following criteria on screening examination to be eligible to participate in the study:

- 3.1.1 Patients must have histologically determined indolent NHL that is relapsed or primary refractory after initial therapy. Indolent NHL includes the morphologic and clinical variants:
 - Follicular lymphoma, grades 1-3a
 - Marginal zone lymphoma (extranodal, nodal, or splenic)
 - All nodal marginal zone lymphomas are eligible
 - Extranodal marginal zone lymphomas of the stomach (gastric MALT lymphomas) may not be candidates for cure with antibiotics or local radiotherapy. Patients who have failed antibiotics or local therapy are eligible for the protocol as long as they have measurable disease \.
 - Splenic marginal zone lymphoma patients may have received prior splenectomy as long as they have measurable disease.
 - Re-biopsy is not mandated at relapse unless there is clinical suspicion about an alternate diagnosis.
- 3.1.2 One or more prior lines of chemoimmunotherapy and/or monotherapy with rituximab or other anti-CD20 antibody. Patients may have had a prior autologous stem cell transplant but not prior allogeneic stem cell transplantation.

CONFIDENTIAL

This document is confidential. Do not disclose or use except as authorized.

Imprime PGG and rituximab for relapsed indolent NHL

November 13, 2018

- 3.1.3 Measurable disease that has not been previously irradiated on CT scans of at least 2 cm, OR if the patient has had previous radiation to the marker lesion(s), there must be evidence of progression since the radiation. Imaging must be completed no greater than 6 weeks prior to study enrollment.
- 3.1.4 ECOG performance status 0-2 (Appendix B, Section 17.2)
- 3.1.5 Absolute neutrophil count ≥ 750 prior to treatment
- 3.1.6 Oxygen saturation $\geq 90\%$, no more than 2 LPM oxygen
- 3.1.7 Serum creatinine ≤ 1.5 X ULN
- 3.1.8 AST ≤ 3 X ULN
- 3.1.9 Total bilirubin ≤ 1.5 X ULN (unless there is lymphoma in the liver)
- 3.1.10 Age ≥ 18 years
- 3.1.11 Ability to understand and the willingness to sign a written informed consent document.

3.2 Exclusion Criteria

Participants who exhibit any of the following conditions at screening will not be eligible for admission into the study.

- 3.2.1 Patients currently receiving anticancer therapies or who have received anticancer therapies within 30 days of the start of study drug (including chemotherapy, radiation therapy, antibody based therapy, etc.). Steroids for symptom palliation are allowed, but must be either discontinued or on stable doses at the time of initiation of protocol therapy.
- 3.2.2 Patients may not be receiving any other investigational agents, or have received investigational agents within 4 weeks of beginning treatment.

CONFIDENTIAL

This document is confidential. Do not disclose or use except as authorized.

- 3.2.3 Patients who have previously received PGG-Betafectin (Betafectin®) or Imprime PGG.
- 3.2.4 Patients, who have had a major surgery or significant traumatic injury within 4 weeks of start of study drug, patients who have not recovered from the side effects of any major surgery (defined as requiring general anesthesia) or patients that may require major surgery during the course of the study.
- 3.2.5 Patients with known leptomeningeal or brain metastases. Imaging or spinal fluid analysis to exclude CNS involvement is not required, unless there is clinical suspicion by the treating investigator.
- 3.2.6 History of severe allergic or anaphylactic reactions to monoclonal antibody therapy or a known hypersensitivity to baker's yeast, unless in consultation with an allergy specialist they are deemed eligible for retreatment with desensitization.
- 3.2.7 Patients with known HIV infection or hepatitis B or C infection. HIV testing is not mandated and is to be performed at the discretion of the treating investigator.
- 3.2.8 Patients with a systemic fungal, bacterial, viral, or other infection not controlled (defined as exhibiting ongoing signs/symptoms related to the infection and without improvement, despite appropriate antibiotics or other treatment).
- 3.2.9 Prior history of another malignancy (except for non-melanoma skin cancer or *in situ* cervical or breast cancer) unless disease free for at least three years. Patients with prostate cancer are allowed if PSA is less than 1. Patients with indolent malignancies under control and which, in the opinion of the treating investigator, are unlikely to be clinically relevant or affect survival during the course of the study treatment and follow-up.
- 3.2.10 Patients should not receive immunization with attenuated live vaccine within one week of study entry or during study period.

CONFIDENTIAL

This document is confidential. Do not disclose or use except as authorized.

- 3.2.11 Female patients who are pregnant or breast feeding, or adults of reproductive potential who are not using effective birth control methods. Women of child bearing potential (WOCBP) or male study participants of reproductive potential must agree to use double barrier birth control method of contraception during the course of the study treatment period and for 3 months after completing study treatment.

WOCBP are defined as sexually mature women who have not undergone a hysterectomy or who are not postmenopausal (no menses) for at least 12 consecutive months. WOCBP must have a negative urine or serum pregnancy test within 7 days prior to administration of treatment.

- 3.2.12 History of noncompliance to medical regimens.

- 3.2.13 Patients who have any severe and/or uncontrolled medical conditions or other conditions that could affect their participation in the study such as:
- New York Heart Association Class III or IV cardiac disease, including pre-existing clinically significant arrhythmia, congestive heart failure, or cardiomyopathy
 - unstable angina pectoris, symptomatic congestive heart failure, myocardial infarction within 6 months of start of study drug, serious uncontrolled cardiac arrhythmia or any other clinically significant cardiac disease

- 3.2.14 Other uncontrolled intercurrent illness that would limit adherence to study requirements.

3.3 Inclusion of Women, Minorities, and other Underrepresented Populations

Women, minorities and underrepresented populations should be eligible for this trial at a similar rate to men and patients not from underrepresented populations. The inclusion and exclusion criteria should not be affected by gender or ethnicity, except for the exclusion of pregnant or lactating women.

4. REGISTRATION PROCEDURES

4.1 General Guidelines for DF/HCC and DF/PCC Institutions

Institutions will register eligible participants with the DF/HCC Quality Assurance Office for Clinical Trials (QACT) central registration system. Registration must

CONFIDENTIAL

This document is confidential. Do not disclose or use except as authorized.

occur prior to the initiation of therapy. Any participant not registered to the protocol before treatment begins will be considered ineligible and registration will be denied.

A member of the study team will confirm eligibility criteria and complete the protocol-specific eligibility checklist.

Following registration, participants may begin protocol treatment. Issues that would cause treatment delays should be discussed with the Principal Investigator. If a participant does not receive protocol therapy following registration, the participant's protocol status must be changed. Notify the QACT Registrar of participant status changes as soon as possible.

4.2 Registration Process for DF/HCC and DF/PCC Institutions

The QACT registration staff is accessible on Monday through Friday, from 8:00 AM to 5:00 PM Eastern Standard Time. If a participant must be registered during off-hours or holidays, call the QACT registration line at [contact] and follow the instructions for registering participants after hours.

The registration procedures are as follows:

1. Obtain written informed consent from the participant prior to the performance of any study related procedures or assessments.
2. Complete the protocol-specific eligibility checklist using the eligibility assessment documented in the participant's medical/research record. **To be eligible for registration to the study, the participant must meet each inclusion and exclusion criteria listed on the eligibility checklist.**

Reminder: Confirm eligibility for ancillary studies at the same time as eligibility for the treatment study. Registration to both treatment and ancillary studies will not be completed if eligibility requirements are not met for all studies.

3. Fax the eligibility checklist(s) and all pages of the consent form(s) to the QACT at [contact].
4. The QACT Registrar will (a) validate eligibility, (b) register the participant on the study, and (c) randomize the participant when applicable.
5. The QACT Registrar will send an email confirmation of the registration and/or randomization to the person initiating the registration immediately following the registration and/or randomization.

CONFIDENTIAL

This document is confidential. Do not disclose or use except as authorized.

5. TREATMENT PLAN

It is expected that treatment will be administered on an outpatient basis. Therapy will consist of four weekly treatments of both Imprime PGG (4mg/kg/dose) and rituximab (375 mg/m²/dose). Imprime PGG will be administered first, followed by a minimum waiting time of 10 to 15 minutes (but maximum of 24 hours +/- 4 hours) before the start of rituximab. Patients with bulky disease or circulating disease $\geq 15,000$ circulating malignant cells/ mm³ will receive allopurinol for prophylaxis of tumor lysis syndrome. Response will be assessed 10 weeks after the completion of therapy by CT scans of the chest, abdomen, and pelvis. Expected toxicities and potential risks for Imprime PGG and rituximab are described in Section 6 (Expected Toxicities and Dosing Delays/Dose Modifications). No investigational or commercial agents or therapies other than those described below may be administered with the intent to treat the participant's malignancy.

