5.3.4 Tumor lysis prevention and management

Participants with bulky disease and/or circulating disease $\geq 15,000$ circulating malignant cells/ mm³ may receive allopurinol 300mg orally daily for 7-10 days starting with the first dose of Imprime PGG and rituximab. Participants deemed at risk for tumor lysis syndrome (TLS) should have their labs monitored per standard practice. The management of established TLs should also follow standard practice.

CONFIDENTIAL

This document is confidential. Do not disclose or use except as authorized.

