6.2 Anticipated Toxicities from Rituximab

A list of the adverse events and potential risks associated with rituximab appear below and will determine whether dose delays and modifications will be made or whether the event requires expedited reporting **in addition** to routine reporting.

- Infusion reactions: including fever, chills, headache, nausea, vomiting, throat irritation, flushing, rash, pruritis, urticaria, dyspnea, increased cough, rhinitis, asthenia, and hypotension, primarily during rituximab infusions which typically respond to an interruption of the infusion and resumption at a slower rate.
 - Fatal Infusion Reactions: Severe and fatal cardiopulmonary events, including angioedema, hypoxia, pulmonary infiltrates, acute respiratory distress syndrome, myocardial infarction, and cardiogenic shock, have been reported. These severe reactions typically occurred during the first infusion with time to onset of 30-120 minutes.
- Night sweats
- Abominal pain, pain, back pain
- Sinusitis
- Diarrhea
- Myalgia
- Arthralgia
- Hypertension
- Dizziness
- Anxiety
- Tumor Lysis Syndrome: tumor lysis syndrome has been reported and is characterized in patients with a high number of circulating malignant cells ($\geq 25,000$ ul) by rapid reduction in tumor volume, renal insufficiency, hyperkalemia, hypocalcemia, hyperuricemia, and hyperphosphatemia.
- Mucocutaneous Reactions: Severe bullous skin reactions, including fatal cases of toxic epidermal necrolysis and paraneoplastic pemphigus, have been reported. The onset of reaction has varied from 1 to 13 weeks following rituximab exposure.
- Metabolic Events: Hyperglycemia, peripheral edema, LDH increase
- Hematologic Events: including lymphopenia, neutropenia, leukopenia, thrombocytopenia with a median duration of approximately 14 days. Transient aplastic anemia (pure red cell aplasia) and hemolytic anemia have been reported.

CONFIDENTIAL

This document is confidential. Do not disclose or use except as authorized.

- Late onset neutropenia, marrow hypoplasia, and prolonged pancytopenia have also been reported.
- **Infectious Events:** B cell depletion and decreased serum immunoglobulins have been associated with an increased risk of bacterial and viral infections. Serious infections (grade 3 or 4) are rare, occurring in approximately 2% of patients.

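### Sections 5 and 5.3.4 give the same patients contradictory instructions on allopurinol, required in one and optional in the other, and nothing says which governs

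*Combined protocol and SAP*

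**What the plan says.** Two sections deal with allopurinol as prevention of tumor lysis.

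- **Section 5, Treatment Plan.** The population is introduced as "Patients with bulky disease or circulating disease" at or above 15,000 malignant cells/mm³. These patients "will receive allopurinol for prophylaxis of tumor lysis syndrome". No dose or duration is given there.
- **Section 5.3.4, Tumor lysis prevention and management.** The population is introduced as "Participants with bulky disease and/or circulating disease" at or above the same count. These participants "may receive allopurinol 300mg orally daily for 7-10 days starting with the first dose of Imprime PGG and rituximab".

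Section 5.3.4 then adds: "Participants deemed at risk for tumor lysis syndrome (TLS) should have their labs monitored per standard practice". It refers the management of established tumor lysis to standard practice as well.

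**The concern.** The drug, the purpose and the cell count are the same in both sections, but one text requires the drug and the other permits it. Tumor lysis is a hazard that the protocol takes seriously: Section 6.2 lists it among the rituximab risks, and Section 6.4 gives rapid tumor lysis as an example of a severe reaction calling for interruption of the infusion. Allopurinol is the only preventive drug that the protocol names for it. Section 5.3.3 requires no hydration, and Section 5 expects outpatient treatment.

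Two things are at stake. The first is whether a patient who meets the criterion gets the preventive drug, which now depends on the section the physician reads. The second is how conduct is judged. Section 13.3 asks that deviations be avoided and Section 12.3 provides for audits against the protocol, but an auditor cannot apply both texts consistently to the same omission. The safety results include the rate of grade III and IV adverse events (Section 14.1), and they are easier to interpret if prophylaxis followed one rule.

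**Working it through.** The plan gives no figure on this point, so the check is a comparison of texts.

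**1. Are the patients the same?** Let A be bulky disease and B a circulating count of at least 15,000/mm³. Section 5.3.4 covers A and/or B, which is the union of A and B. Section 5 covers A or B, which on the ordinary inclusive reading is the same union. An exclusive reading would drop patients with both features from the Section 5 requirement, which is hardly intended. Even then, the conflict would remain for everyone with one feature only.

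**2. Is the instruction the same?**

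| | Section 5 | Section 5.3.4 |
|---|---|---|
| Drug | allopurinol | allopurinol |
| Count threshold | 15,000/mm³ | 15,000/mm³ |
| Verb | will | may |
| Dose and duration | none | 300 mg daily, 7-10 days |

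Only the verb conflicts. The regimen is attached to the optional version, so the mandatory version has none of its own.

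**3. Is *may* just loose drafting?** The neighbouring subsections grade their wording. Premedication is stated as something that will be given (5.3.1). Antibiotics and hydration are stated as not required (5.3.2, 5.3.3). Transfusions are left to the physician's discretion (5.3.5). Read beside these, *may* is naturally taken as optional.

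**4. What follows for a qualifying patient?**

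| Action | Against Section 5 | Against Section 5.3.4 |
|---|---|---|
| Allopurinol given | complies | complies |
| Allopurinol omitted | departs | complies |

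**5. Does another passage settle it?** None was found. The rest of Section 5.3.4 covers laboratory monitoring and established tumor lysis. Section 6.4 covers interruption of infusions. Neither says whether prophylaxis is required.

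**6. Can practice diverge?** Section 4.1 foresees more than one institution: "Institutions will register eligible participants with the DF/HCC Quality Assurance Office for Clinical Trials (QACT) central registration system". Section 11.3 speaks of each investigative site. Section 5.2 names a single centre for giving rituximab, but the point does not need several sites, because two physicians at one centre can read different sections.

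**7. Does the primary analysis depend on it?** No. The design uses n = 25, a cut-off of 11 responses, and rates of 30% and 50%. The exact binomial probability P(X ≥ 11 | n = 25, p = 0.50) is 0.788, which reproduces the stated 0.79. P(X ≥ 11 | n = 25, p = 0.30) is 0.098. Allopurinol enters neither calculation.

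**The case against.** The best defence is that the two sections can be read together: Section 5 sets the requirement and Section 5.3.4 supplies the regimen. A physician who gives the drug satisfies both. On this view the fault is one badly chosen verb. Other safeguards also remain: laboratory monitoring of patients at risk, blood counts and chemistries at each weekly treatment (Section 9), and interruption of the infusion for rapid tumor lysis. No analysis turns on the point.

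Much of this stands. The safeguards are real and limit the consequence, and the absence of any effect on the efficacy analysis is conceded. The joint reading is possible, but nothing in the text confirms it, and the graded wording elsewhere in Section 5.3 points the other way. Monitoring and interruption do not answer whether the preventive drug is required.

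The objection also disposes of a stronger reading that a reader might infer: that a site can leave the drug out and still be following the protocol. It cannot. Omission agrees with Section 5.3.4 only and departs from Section 5. The supportable claim is that a physician relying on Section 5.3.4 alone would think omission permitted.

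**Conclusion.** The contradiction holds. Two operative passages in the current protocol give different instructions to the same patients on preventing a serious toxicity, and neither is given precedence. It should be classed as an internal contradiction, wrong as written, and not as a choice of design. The conclusion rests on the inclusive reading of *or* and on the ordinary meaning of *will* and *may*.

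Its size cannot be stated. The documents give no number of qualifying patients, no expected rate of tumor lysis and no estimate of how far allopurinol lowers it. Bulky disease is also not defined in the text available, which is a separate point.

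Two further inferences are not supported:

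- *That Section 6.2 sets a competing threshold.* Its count of 25,000 belongs to a description of reported tumor lysis, "characterized in patients with a high number of circulating malignant cells", within a list of rituximab toxicities. It sets no rule for prophylaxis, and both operative passages use 15,000.
- *That the suspension rule measures the risk.* Section 14.2 suspends the study for review at three participants with grade 4 non-hematologic toxicity. A grade 4 tumor lysis event would presumably count, as would any other such event. Without an event rate, the rule says nothing about how likely the inconsistency is to bring a suspension nearer.

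**What to change.** The investigators should reconcile Sections 5 and 5.3.4 into one statement that says whether allopurinol prophylaxis is required or discretionary and to which patients it applies. The regimen should be attached to that statement, and the other section should refer to it and not restate it. Which rule is right is a clinical decision for the investigators, and this review takes no position on it. Once one rule stands, whether an omission is a deviation is settled too.

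The cost is about one sentence in a protocol amendment, with the IRB approval that Section 13.1 requires. The sample size, the decision rule and the visit schedule do not change.

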5.1 Imprime PGG Administration

The study drug Imprime PGG will be administered by intravenous bolus infusion through a low protein binding 0.22-micrometer in-line filter at a dose of 4 mg/kg (actual body weight) over at least 2 hours (longer infusion times are required for subjects over 75 kg). The dosing frequency will be every 7 days for a total of 4 weeks. Participants will be pre-medicated according to institutional standards for rituximab prior to administration of either drug. Imprime PGG will be provided by Biothera. The drug product, Imprime PGG, is a sterile solution for IV administration. It is supplied in 20-mL or 50-mL vials containing PGG Beta Glucan at a nominal concentration of 1 mg/mL in 0.14 M sodium chloride, 0.011 M sodium citrate, pH 5.0-7.5.

5.2 Rituximab administration

Rituximab from a commercial supply will be administered IV at a dose of 375 mg/m² every 7 days for 4 weeks. Actual body weight will be measured prior to each Rituximab infusion to calculate the BSA and dose for each infusion.. If the infusion cannot be completed within 1 day, the patient is allowed to receive the remainder of the infusion the following day as long as the dose is administered within 2 consecutive days.

Rituximab will be administered at DFCI per Dana-Farber Harvard Cancer Center institutional guidelines.

Dana-Farber Harvard Cancer Center institutional guidelines include:

CONFIDENTIAL

This document is confidential. Do not disclose or use except as authorized.

Imprime PGG and rituximab for relapsed indolent NHL

November 13, 2018

- Participants will be pre-medicated with hydrocortisone 100 mg IV, acetaminophen 650 mg, and diphenhydramine 25 mg PO, or their equivalents, prior to each dose.
- No specific prehydration is required.
- The first infusion will begin at an initial rate of 50 mg/hour for the first hour. If hypersensitivity or infusion-related events do not occur, the rate will be increased in 50 mg/hour increments every 30 minutes until a maximal rate of 400 mg/hour.
- On subsequent infusions the initial rate in the absence of hypersensitivity will be 20 percent of the total dose over 30 minutes, followed by the remaining 80 percent of the total dose over 60 minutes.
- Vital signs should be checked approximately every 15 minutes during the first hour of infusion, then approximately once an hour or prior to any infusion rate change until completion of the infusion.
- Infusion should be temporarily discontinued for a temperature > 101.3°F, mucosal edema, or >30 mm Hg decrease in systolic blood pressure.
- An additional 25 mg of benadryl IV should be given.
- Infusion may resume after symptoms resolve a 50% of the rate infusing at the time of the event.

5.3 General Concomitant Medication and Supportive Care Guidelines

5.3.1 Pre-medications

Participants will be premedicated with hydrocortisone 100 mg IV, acetaminophen 650 mg, and diphenhydramine 25 mg PO, or their equivalents, prior to each dose. No specific prehydration is required.

